a side effect concern. In other clinical studies, daily doses of 5 mg (i.e., 5 times the daily in the proposed study for alcohol problems) were administered to 60 men for 6 months with no adverse effects beyond those seen at the more commonly used daily dose of 0.5 mg (Avodart, Prescribing information 2012, GlaxoSmithKline). Depression has been reported as a potential side effect of the 5AR inhibitor finasteride in several small retrospective case series (Hirshburg, Kelsey et al. 2016). In the only prospective study examining mood in 128 men treated with finasteride for alopecia, the Beck Depression Inventory (BDI) score increased minimally from 12.11 to 12.80 after 2 months treatment (Rahimi-Ardabili, Pourandarjani et al. 2006). In our current study of dutasteride in men we observed a decrease in BDI scores over the 12-week study period in both dutasteride and placebo arms. A recent large retrospective study of 90,000 men who initiated treatment with a 5α reductase inhibitor (finasteride or dutasteride) during the period 2003-2013 and matched controls found no increased risk of suicide associated with medication but an increased risk of self-harm events (18 per 10,000 exposed vs. 14 per 10,000) and incident depression (194 per 10,000 exposed vs. 137 per 10,000) during the initial 18 months of treatment (Welk, McArthur et al. 2017). In view of these reports of the potential for 5α reductase inhibitors to increase depressive symptoms, we will use the physician's health questionnaire (PHQ-9) to screen for clinical depression at every study visit. The PHQ-9 is a validated 9-item self-report measure of depressive (Ware, Kosinski et al. 1996, Kroenke, Spitzer et al. 2001), a response of 1 or greater on item 9 related to suicidal thoughts will trigger a clinical evaluation by study physician or nurse regarding safety.

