Naltrexone is FDA approved for the treatment of alcohol dependence as well as for opioid dependence. Naltrexone has also been shown to reduce heavy drinking in multiple RCTs (Maisel, Blodgett et al. 2013, Jonas, Amick et al. 2014). Naltrexone is an antagonist of the μ-opioid and κ-opioid receptors is thought to reduce alcohol craving and heavy drinking by blocking the endogenous opioid system and thereby reducing dopamine release in response to the anticipation of or use of alcohol. Naltrexone has no abuse potential. In subjects with dependence on opioids who have recently used opiates naltrexone will precipitate withdrawal symptoms. The most common side effects of naltrexone in a large open label safety study (Croop, Faulkner et al. 1997) in 570 subjects with alcoholism (Revia, Prescribing information 2013, Barr Pharmaceuticals) were: nausea (10%), headache (7%), dizziness (4%), nervousness (4%), fatigue (4%) insomnia (3%), vomiting (3%), anxiety (2%) and somnolence (2%). A prior FDA black box warning related to possible hepatotoxicity based on naltrexone use at 300 mg / day for obesity has subsequently been removed based on extensive experience with naltrexone 50-100 mg/day for alcohol dependence. Naltrexone is a pregnancy class C medication (animal data suggest teratogenic potential, but no human data available). To be eligible for participating in this study women of reproductive potential will be required to agree to use effective contraceptive practices.

Interaction of Medications and Alcohol: Neither dutasteride or naltrexone produce clinically significant additive interactions with alcohol on CNS depressant effects. Dutasteride and naltrexone are both safe in the setting of ongoing alcohol use.

Blood and Urine Collection: These procedures are performed in large measure for baseline screening to safeguard that patients with untreated medical conditions are not enrolled and at subsequent visits to monitor medication safety, document urine drug use screening and verify absence of pregnancy. Additional bloods are drawn for research measures of alcohol use and dutasteride effects. These procedures should add no risks other than those normally associated with these procedures, e.g., pain and bruising as a consequence of venipuncture.

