AE monitoring. The study nurse will use the SAFTEE instrument to screen for adverse events at each treatment visit. The P.I. will evaluate every moderate or severe adverse event and determine whether it affects the risk/benefit ratio of the study and whether modifications to the protocol or informed consent form are required. The principal

investigator (and, in his absence, physician co-investigators) will differentiate serious from non-serious adverse events.

A Serious Adverse Events Monitoring Form will be used by study staff to provide information about all serious adverse events (expected and unexpected including not study related), how they were handled, and their potential relationship to study participation and a sign-off by appropriate supervisory personnel. Patients who experience a significant psychiatric or medical problem requiring an overnight hospitalization at an acute care facility will be considered to have experienced an SAE. Serious Adverse Events also include adverse events that result in death, a persistent or significant disability/incapacity or result in a congenital anomaly/birth defect.

Serious adverse events (SAEs) and other serious unanticipated events that are possibly related to the study interventions will be reported within 48 hours of study team knowledge of the SAE to the 1) UCHC IRB / Office of the Vice President for Research, 2) the study DSMB, and 3) the NIAAA project officer. All other SAEs, unanticipated events and non-serious adverse events (AEs) during the treatment will be reported to the UCHC IRB, as well as to the NIAAA on an annual basis. SAEs, AEs, and unanticipated problems will be managed consistent with UConn Health IRB guidelines.

Other adverse events will be monitored during study visits or phone calls with participants and reviewed weekly at study staff meeting. An ongoing database of adverse events will be maintained by the study staff. Aggregate data on reports of adverse events will be provided to the DSMB members on a semi-annual basis as part of their semi-annual review with the study staff and PI of data and patient safety monitoring. The following information will be considered in the periodic safety report:

- Number of patients who have completed the study.
- Dropout rates and reasons for the dropouts.
- Summary of adverse events.
- Any other relevant information

The annual report to the NIAAA program officer will include

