- Confirmation of adherence to the data and safety monitoring plan;
- Summary of all AEs;
- Summary of any data and safety monitoring issues that occurred since the previous reporting period;
- Description of any changes in the research protocol or the data and safety monitoring plan that potentially affect risk;
- Summary of all new IRB approvals during the report period.

Any patients thought to be at risk from drinking or psychiatric or medical disorders during treatment or the follow-up period will be referred to services at UCONN Health or to other local health service providers.

Data Monitoring. Data entry will occur at the time of visit via REDCap directly by staff or study subjects (with supervision by staff). Other data not entered at time of visit will be doubly entered via REDCap feature to assure accuracy of entry. All study staff involved in data entry are blind to treatment condition. The PI will have primary responsibility for data accuracy and compliance with protocol.

A Data Safety and Monitoring Board (DSMB) for the study will be established prior to enrollment of patients. This committee will be asked to review semi-annually study data regarding enrollment, safety and adverse events. The committee may make recommendations for early stoppage of the trial based on review of study data. DSMB members will be provided with semi-annual reports to include data that inform progress of the study, including recruitment data, and adverse events data. These data will be used to decide whether to 1) continue recruitment as planned, 2) continue with a protocol amendment, or 3) stop recruitment pending investigation. The DSMB will typically hold meetings electronically or by conference call.

Study suspension / stopping. A decision to discontinue the study will be based primarily on consideration by the DSMB of study related serious adverse events (SAE's). DSMB members will receive a copy of the Serious Adverse Events Monitoring Form within 48 hours of study team knowledge of the SAE, at which point DSMB members will make one of two recommendations: 1) continue recruitment and treatment as planned; 2) schedule a formal meeting within one week to determine if the study should: a) continue study unchanged; b) continue recruitment after a protocol amendment; or c) stop recruiting and if appropriate treatment pending further investigation.

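### Section 3.C gives no single clear rule on which SAEs reach the DSMB promptly, and its listed SAE criteria omit life-threatening events that need no overnight stay

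*Combined protocol and SAP*

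**What the plan says.** All the reporting rules are in section 3.C, Data and Safety Monitoring Plan.

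- **Form (AE monitoring).** The Serious Adverse Events Monitoring Form collects "information about all serious adverse events (expected and unexpected including not study related".
- **Definition (AE monitoring).** A patient with a significant psychiatric or medical problem "requiring an overnight hospitalization at an acute care facility will be considered to have experienced an SAE". The text adds: "Serious Adverse Events also include adverse events that result in death, a persistent or significant disability/incapacity or result in a congenital anomaly/birth defect".
- **48-hour route (AE monitoring).** The rule covers SAEs and also unanticipated events of a serious kind: those "possibly related to the study interventions will be reported within 48 hours of study team knowledge of the SAE". There are three recipients: the IRB, the DSMB and the NIAAA project officer.
- **Remaining events (AE monitoring).** "All other SAEs, unanticipated events and non-serious adverse events (AEs) during the treatment will be reported to the UCHC IRB", and also to NIAAA yearly. The DSMB is not named here.
- **Stopping (Study suspension / stopping).** A decision to discontinue rests mainly on the DSMB's view of SAEs that are related to the study. The next sentence says that "DSMB members will receive a copy of the Serious Adverse Events Monitoring Form within 48 hours of study team knowledge of the SAE", after which members recommend either continuing or holding a formal meeting.
- **Periodic data (AE monitoring and Data Monitoring).** The DSMB gets aggregate adverse event data twice a year.

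Among the risks of dutasteride, section 3.A.3 cites a retrospective study of men starting a 5-alpha reductase inhibitor that found "an increased risk of self-harm events (18 per 10,000 exposed vs. 14 per 10,000" in matched controls).

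**The concern.** The DSMB's continue-or-meet recommendation is triggered by receipt of the form. Which forms are sent therefore decides which events get that review.

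Under AE monitoring, the gate to prompt notice is a causality judgement made within the study team, under double-blind conditions. In heavy drinkers, alcohol is a ready alternative explanation for an injury, a seizure or a self-harm event. If events rated unrelated are held back from case-level review, an independent board is less able to notice a pattern across cases that each looked explicable alone.

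The definition has a similar effect one step earlier. An event outside the SAE criteria does not generate the form at all. A self-harm event that threatened life, was treated in an emergency department and was followed by same-day discharge without lasting disability meets none of the listed criteria.

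**Working it through.** No sample size, power or event count is involved, so this is a check of text against text.

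**Step 1. Definition.** The listed routes to an SAE are four: overnight acute-care hospitalization, death, persistent or significant disability or incapacity, and congenital anomaly or birth defect. Take an event that was life-threatening, needed no overnight stay and left no lasting disability. It fails all four. No listed criterion refers to threat to life or to medical importance.

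**Step 2. Two readings of the stopping paragraph.**

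- *Wide reading.* The form covers all SAEs, including unrelated ones, so the DSMB receives a form for every SAE within 48 hours.
- *Narrow reading.* The SAE in that sentence is the study-related SAE of the sentence before it, so the DSMB receives forms only for those.

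**Step 3. What the DSMB receives, by type of event.** Study-related and possibly related are treated as the same here, which is an assumption.

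| Event | AE monitoring | Stopping, wide | Stopping, narrow |
|---|---|---|---|
| SAE, possibly related | 48 hours | 48 hours | 48 hours |
| SAE, judged unrelated | DSMB not listed | 48 hours | No case-level notice |
| Life-threatening, outside the four criteria, unanticipated and possibly related | 48 hours, if classed as a serious unanticipated event | No form specified | No form specified |
| Life-threatening, outside the four criteria, anticipated or judged unrelated | DSMB not listed | No form specified | No form specified |

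The second row is the ambiguity. On the wide reading, the two parts of 3.C disagree. On the narrow reading they agree, but no case-level notice of unrelated SAEs is specified for the board at any time. Either way the text needs a decision.

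The fourth row is the definition gap. Self-harm is a risk that the protocol itself names, so staff could reasonably class it as anticipated.

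**Step 4. Length of the delay.** Where no 48-hour notice applies, the remaining route is the aggregate summary. Two summaries a year means an interval of 12 / 2 = 6 months, so an event just after one summary could wait about 6 months for the next. That summary is aggregate, and 3.C specifies no SAE listing or narrative for it.

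**Step 5. Period covered.** Side effects are collected with the SAFTEE at the 3- and 6-month follow-up visits (Table 2, Schedule of Assessments; section 2.C.6.b.4). The 48-hour sentence has no time limit. The sentence on remaining events refers to the treatment period, and it is unclear whether that limit applies to SAEs or only to non-serious events.

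**The case against.** The strongest reply is that the two parts of 3.C do not conflict. The 48-hour sentence on stopping directly follows a reference to study-related SAEs, and read that way it matches AE monitoring. This stands as far as it goes: a reader might infer a flat contradiction, and the documents support only an ambiguity.

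Second, the board has other sources. It receives adverse event data twice a year, may recommend early stopping on review of study data, and can ask the pharmacy for unblinding. Possibly related serious unanticipated events have their own 48-hour route, even outside the four criteria. A reader might infer that the DSMB would miss these events altogether; these provisions do not support that. What remains is the lack of prompt, case-level notice. A request for unblinding also presupposes that the board has already seen a concern.

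Third, the definition is not worded as exclusive, and the principal investigator separates serious from non-serious events. SAEs are also to be handled in line with the institution's IRB guidelines. Those guidelines are not reproduced, so they cannot be assumed to fill the gap, and investigator discretion is not a stated criterion.

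Fourth, the protocol has safeguards: the PHQ-9 with a trigger on its suicidal-thoughts item, withdrawal screening at every visit, exclusion for a history of serious withdrawal, and an opioid check before a change of medication. These reduce or detect events. They do not settle who is told, or when.

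**Conclusion.** The point holds as a reporting gap that wording can close. AE monitoring and Study suspension / stopping do not state one rule for SAEs judged unrelated, and the listed criteria have no life-threatening criterion. The consequence is that the DSMB may see such events only in aggregate, up to about 6 months later, instead of case by case within 48 hours. This rests on the text of 3.C alone and assumes that the uncited content of the IRB guidelines does not change it.

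Some stronger inferences are not supported:

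- **An expected number of self-harm events.** A reader might multiply the cited rate by the 190 planned patients. That rate is for exposed men during the first 18 months of treatment. This trial includes women, treats for 12 or 24 weeks, and starts half its patients on placebo.
- **The prior trial.** A reader might infer that these rules would have sent its board nothing. Section 2.B.2 reports no study-related serious adverse effects, but not how many SAEs occurred or what its board received.
- **A year against 48 hours.** This compares different recipients: the yearly report concerns the IRB and NIAAA, not the DSMB.
- **Psychiatric admissions.** A reader might infer that these fall outside the hospitalization criterion. It expressly covers psychiatric problems, so that is speculation.

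**What to change.** In section 3.C:

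1. Make AE monitoring and Study suspension / stopping agree. State in both that the DSMB receives the SAE Monitoring Form within 48 hours of study team knowledge for every SAE, whatever the causality rating.
2. State that this applies through the 6-month follow-up visit.
3. Add life-threatening events to the SAE definition, whether or not there is an overnight stay, and match the form to it.

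The cost is an edit to 3.C and the form, and a few more forms to the DSMB, many of them reflecting drinking rather than drug. The causality rating stays on the form, so the board can weigh it.
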